a point drawn 4 cm directly vertical from the nipple to ensure accurate positioning, and will be secured in place. The outline of the cancer on the breast surface will be drawn by the surgeon. Four injections of 0.02 ml of methylene blue dye (Methylene Blue Injection, 1% Akorn, Inc Lake Forest, IL) will be made by the surgeon using a 21 gauge needle of appropriate length to create spots to delineate the cranial, caudal, medial and lateral tumor margins. An additional methylene blue dye injection will be made to delineate the superficial margin. The fifth needle port will then be partly detached so that a second needle can be placed through this port into the MRI defined center of the cancer and a hook wire will be placed inside this needle and deployed in the center of the tumor. The BCL will then be removed and the distances from the medial, lateral, cranial and caudal edges as determined by the BCL will be compared to the edge locations determined by the optical scan/tracker method.

The surgeon will then perform either a breast conserving tumor resection or a mastectomy. The objective of the breast conserving resection will be to remove approximately 1 cm of normal feeling breast tissue around all of the palpable tumor edges as per standard-of-care. For breast conserving resections, the specimen volume will be determined by water displacement and specimen scanning using the GO!Scan. The location of the 4 horizontal blue dye spots in the specimen will be identified by the surgeon with black silk sutures; the location of the superficial blue dye spot will be marked with a white VICRYL suture. The specimen surfaces will be inked with 6 different colors, as per standard Dartmouth protocol. Specimen mammograms will be obtained and then the specimen will be sent to Pathology.

Mastectomy specimens will be sent to Pathology and inked with blue ink on the superficial surface and black ink on the deep surface. The surgeon will then perform a breast conserving resection on the mastectomy specimen in Pathology. The goal of this procedure will be to remove approximately 1 cm of normal tissue around the tumor and to identify the blue dye spots and place marking sutures in the same way that they will be placed on breast conserving resection specimens. The specimen volume will be determined, margins will be inked with 6 colors and a specimen mammogram will be obtained.

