In Pathology, the specimen will be cut along the horizontal plane defined by the black silk sutures. The pathologist will place black-inked pins through the middle of the blue dye spots. A photo will be taken of the tissue slice showing the tumor in the middle with the 4 blue

dye spots with pins in place. When tissue sections are cut, the black ink from the pins will appear on the sections, allowing the pathologist to measure the distance from the pin to the tumor. An additional cut will be made to include the white vicryl suture, in a plane perpendicular to the one defined by the black silk sutures. A black inked pin will be placed through the middle of this superficial blue spot, a photo will be taken of the tumor and this pin, and a section will be cut so the pathologist can measure the distance from this pin to the tumor.

Margins for invasive cancers will be considered positive if cancer cells are present at any of the edges of the specimen slices. Margins will be considered positive for DCIS if there are tumor cells < 1 mm from the edge. The distance to the nearest margin will be determined in all cases.

Section 5. POTENTIAL TOXICITY

Supine MRIs are administered according to standard-of-care practice for prone breast MRI and represent no more additional risk than would be experienced by women receiving these exams as part of their (non-research) breast care. The risk of contrast enhanced MRI is very low, reflecting the minute risk of life-threatening allergy and development of nephrogenic sclerosis related to gadolinium-based intravenous contrast. Patients deemed to be at higher risk for gadolinium-induced nephrogenic sclerosis because of compromised renal function will not be eligible for participation. Patients who experience a significant allergic reaction to gadolinium-based intravenous contrast at the time of their clinical prone MRI will also be considered ineligible for study participation.

Optical scans will be performed using a GO!Scan 3D optical scanner (Creaform, Levis, Québec, Canada). This scanner is able to scan the entire breast in 1 minute. It uses white light (LED) to form the image, like a flashlight. No anticipated risks are associated with the use of this scanner.

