Supine MRI images will be used to create a Breast Cancer Locator using 3-dimensional printing. The printed product will include a surface that will fit on the breast, a cut-out for the nipple and for a spot 4 cm directly vertical from the nipple (to ensure that the BCL is positioned accurately on the breast surface), a cut-out for the surgeon to draw the tumor image on the breast surface, and 5 cylinders to guide needle injections of dye to define the cancer edges. A needle will be placed in each cylinder. The depth and angle that the needle passes into the breast is controlled by the angle and length of the cylinder. Needles will be 21 gauge in diameter and of sufficient length. A syringe will be included which will allow accurate injection of 0.02 ml of methylene blue dye. The surgeon will inject the blue dye at each site, creating a 1 cm diameter blue spot in the breast parenchyma. The spots will be made 1 cm away from the medial, lateral, cranial and caudal tumor edges as defined by the supine MRI. All of these spots will be in the same cross-sectional plane. This plane will be perpendicular to a line formed from the center of the tumor to surface of the skin at the location where the tumor is closest to the skin. The fifth cylinder will allow the surgeon to inject methylene blue dye 1 cm superficial to the tumor and will allow a second needle to be placed from the skin into the MRI defined center of the tumor.

The BCL will also contain the printed surface of the tumor, colored differently, which will be connected to the surface of the tumor locator by a removable cylinder. This form will enable the surgeon to have a visual model of the cancer in the breast.

Each BCL will undergo quality assurance testing prior to use. Defined length and bore needles will be placed into each of the cylinders and the distance from the tip of the needle to the tumor will be measured. A BCL will only be used if this distance is within 2 mm of the

expected distance as calculated by the MRI model. In the case of irregularly shaped tumors this distance may be greater than 1 cm. The tumor locator will be sterilized using standard microwave techniques for use in the OR.

Sections 7 and 8. Clinical ENDPOINTS AND STATISTICAL ANALYSIS

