Our primary objective is to determine the accuracy of the Breast Cancer Locator (BCL). The primary outcome measure is the distance measured by Pathology from the tumor edge to the center of the ink spots, as marked by the black inked pins. Five (5) measurements will be made per patient. The BCL will be considered accurate if all 5 measurements are > 0 cm from the tumor edge.

As discussed in the Introduction, we expect that in approximately 5% of patients the pathologically determined tumor diameter will be at least 2 cm greater than the MRI defined diameter; thus even if a 1 cm margin around the MRI defined tumor edge was excised, a positive margin (a distance of zero or less) would be expected in 5% of patients. We will evaluate the accuracy of the BCL after the first 10 patients. If the BCL is accurate in $< 80\%$ of patients, we will make modifications in the locator and test an additional 10 patients. If it remains inaccurate, additional modifications may be made and additional patients may be accrued to this study up to a maximum of 50 patients. If the measurements are accurate in 80% of patients or more of the patients in a test cohort of ten patients, we will accrue an additional 10 patients to confirm the finding. Once the accuracy is determined to be $\geq 80\%$ in 20 patients we will terminate accrual.

The modifications we make in the BCL will be based on a thorough review of each case that was inaccurate. We will review every step in the process, including the definition of the cancer edges by Radiology, the quality assurance testing of the manufactured BCL (Section 6, P. 13), the pin placement in the ink spots and edge measurement by Pathology, and whether the cases represent unusual cancers where the pathologic extent of the tumors exceeds the extent visible on MRI (e.g., Infiltrating lobular cancer). We may discover an unforeseen design flaw in the methodology or product manufacture that will only become evident once we start to use it.

Annually at Dartmouth we care for approximately 300 patients with invasive ductal cancer and 100 patients with DCIS. Approximately 2/3 of these patients (266) will undergo breast conserving surgery. Approximately 1/4 of these patients will have palpable tumors (67). We anticipate that it will be possible to accrue one half (33) of these patients per year. Thus, we expect that it will take 8 months to complete accrual of 20 patients.

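### The primary rule (all five distances above zero) shows that the dye spots clear the tumor, not that they landed where planned, and no analysis against the planned distance is specified

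*Combined protocol and SAP*

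**What the plan says.** Section 2 sets the aim of testing whether the locator (BCL) defines the cancer edges accurately. It makes the distance from spot center to cancer edge the primary objective.

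Sections 7 and 8 turn this into a score per patient: "Five (5) measurements will be made per patient" and "The BCL will be considered accurate if all 5 measurements are > 0 cm from the tumor edge". The score drives the decisions at 80% of the first 10 and 80% of 20 patients. On failures they say: "The modifications we make in the BCL will be based on a thorough review of each case that was inaccurate".

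Section 6 gives each spot an intended position: "The spots will be made 1 cm away from the medial, lateral, cranial and caudal tumor edges as defined by the supine MRI". It adds a bench check, "A BCL will only be used if this distance is within 2 mm of the" distance expected from the MRI model, and notes: "In the case of irregularly shaped tumors this distance may be greater than 1 cm". A planned distance therefore exists for every cylinder, but the plan uses it only before surgery.

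Section 4 says how spots reach the pathologist. A breast conserving resection aims to "remove approximately 1 cm of normal feeling breast tissue around all of the palpable tumor edges as per standard-of-care". In Pathology, "the specimen will be cut along the horizontal plane defined by the black silk sutures".

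**The concern.** A placement-accuracy result should say how far the marks lie from where they were meant to be. The rule says only that none lies in or on the tumor. A device with large errors away from the tumor, or with inward errors smaller than the planned offset, scores the same as a perfect one.

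Sections 7 and 8 specify descriptive statistics for the tracker distances and specimen volumes, but no summary of the primary distances against plan. The tracker comparison, with its 5 mm criterion on the mean, is made on the skin against another localization method. It may reveal some in-plane shifts, but it checks neither the dye spots nor their depth and does not enter the 80% decision. The case review is described only for patients who fail the rule.

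This matters because the accuracy information is meant to support a larger trial in non-palpable cancers, where the surgeon cannot fall back on palpation. A clearance rate alone would not tell that trial's designers how large the placement error can be.

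**Working it through.** **The plan's own input.** The Introduction supports roughly 5% failures from MRI underestimation with 1/27 = 3.7%, 1/60 = 1.7% and 2/68 = 2.9% (pooled 4/155 = 2.6%). So 5% is rounded up. No alpha, power or in-body placement error is stated, so there is no such figure to reproduce.

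**1. Error that the rule tolerates for one recovered spot.** Distance to the tumor edge ≥ planned distance − size of misplacement.
- Planned 10 mm, MRI and pathology edges equal: any misplacement under 10 mm leaves a distance above 0.
- Median underestimate of diameter 5 mm, or 2.5 mm per side: 10 − 2.5 = 7.5 mm.
- Median overestimate of diameter 4 mm, or 2 mm per side: 10 + 2 = 12 mm.

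A single spot that drifts 9 mm inward reads 1 mm, lies well inside the specimen, and passes.

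**2. Whole-device shifts.** Assumed model: spherical tumor of radius R; four in-plane spots and one superficial spot at R + 10 mm from its center; all moved by one vector. Reading = distance from the shifted spot to the center, minus R. Tumor diameters are 15, 20 and 30 mm.

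| In-plane shift | Share of directions passing if all spots are recovered (15 / 20 / 30 mm) | Farthest spot center from tumor, minimum over directions and sizes |
|---|---|---|
| 9 mm | 100 / 100 / 100% | 17.0 mm |
| 12 mm | 55 / 50 / 45% | 19.5 mm |
| 15 mm | 44 / 36 / 25% | 22.2 mm |

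For a 20 mm tumor, a 15 mm shift at 45 degrees reads 22.4, 22.4, 4.2, 4.2 and 15.0 mm and would count as accurate.

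**3. Which of these would be seen.** A spot is 1 cm across (Section 6), so one centered more than 15 mm out lies wholly beyond an idealised 10 mm resection. In this model every in-plane shift above about 6.6 mm puts at least one spot there. A 5 mm shift along an axis of a 20 mm tumor reads 5 and 15 mm on that axis and 10.6 mm on the other (√(20² + 5²) − 10), so it can be recovered and pass. The 9 to 15 mm rows therefore apply mainly to mastectomy or wider specimens.

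**4. Depth.** For a superficial shift z smaller than R, the in-plane reading is R + 10 − √(R² − z²). With R = 10 and z = 7 this is 20 − √51 = 12.9 mm, and the fifth spot reads 17 mm: accurate, if all spots are recovered. With z ≥ 10 mm the cut plane contains no tumor section, so the four in-plane distances cannot be taken.

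**5. Effect of counting lost spots as not meeting the rule.** Let p = 0.95 × (1 − loss), with loss the assumed share of patients losing a spot. The probability of at least 8/10 and then at least 16/20, without modification, is Σ over k = 8 to 10 of P(X₁ = k) × P(X₂ ≥ 16 − k), where X₁ and X₂ are Binomial(10, p).

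| Loss | p | P(both gates) |
|---|---|---|
| 0% | 0.95 | 0.987 |
| 5% | 0.9025 | 0.917 |
| 10% | 0.855 | 0.770 |
| 20% | 0.76 | 0.382 |

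**The case against.** The strongest reply is that the rule is reasoned. The 1 cm offset comes from MRI-pathology data, a distance of zero or less is tied to a positive margin, and the positive margin rate is the expected main outcome of the next trial. The continuous distance is already the primary measure, so departure from a 1 cm plan can be read off unless the tumor is irregular. This stands as a defence of the rule as a clearance measure. It does not supply the missing comparison with plan.

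Three stronger readings are tempting, and the documents do not support them.

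- A reader might infer that shifts of 12 to 15 mm would routinely pass. In a resection of about 1 cm at least one spot would usually be missing, so needing five recovered spots gives the rule an indirect upper limit in those patients.
- A reader might take the 2 mm bench limit as the standard for in-body error and call the tolerated error five times too large. That limit is a manufacturing check, and nothing says the two should match.
- A reader might infer that lost spots leave the decision open, for example 7/10 = 70% against 7/8 = 88% if two incomplete patients are dropped. The rule requires all five measurements and the cohorts are fixed at 10 and 20, so the text already implies that an incomplete patient is not accurate. No passage suggests exclusion.

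It is also fair to say that measured minus planned distance mixes device error with MRI-pathology mismatch, and that a correctly placed spot sits near the planned specimen edge and can be lost to a close resection. Both limits are carried into the fix.

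**Conclusion.** The point holds in this form: the primary rule is a legitimate clearance criterion, but alone it cannot show placement accuracy, and nothing else in the plan measures the dye spots against their intended positions. The tolerated error for a recovered spot planned 10 mm out is anything under 10 mm, or 7.5 to 12 mm at the Introduction's median size differences. This follows from the plan's own figures. Larger passing errors depend on the assumed spherical tumor and rigid shift, and on the spots being recovered.

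The rule is not blind to error. It catches inward errors as large as the planned offset, and in breast conserving specimens large outward errors often appear as missing spots. The scoring of those patients needs an explicit sentence, but that part is a clarification. All placement errors and loss rates used here are assumptions.

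**What to change.** 1. Keep the above-zero rule for the 80% decision and describe it as tumor clearance.
2. Report beside it, as placement error, pathology distance (negative if inside tumor) minus the MRI-model planned distance for each spot. Give mean signed error, SD and limits of agreement by direction, allowing for five spots per patient, and each patient's largest absolute error. The mean alone is not enough, because shifts in different directions cancel across patients. State that this error includes MRI-pathology size mismatch, a median of about 2 to 2.5 mm per side.
3. Add a clarification such as: A patient with any unrecovered or unmeasurable spot, including no tumor in the cut plane, stays in the cohort denominator and does not meet the rule; the cause (device error or a close resection) is reviewed before the locator is modified; a sensitivity analysis excludes losses not due to the device.

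A two-sided tolerance, and a review trigger for large errors that still clear the tumor, are optional and for the sponsor to set and justify beforehand.

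**Cost.** Items 1 and 2 need only wording and analysis of data already produced, since the planned distances exist for the bench check. Item 3 makes the literal reading explicit. If spots are lost, the chance of passing both gates without modification falls from 0.987 to 0.917, 0.770 or 0.382 at assumed patient-level losses of 5, 10 or 20%.

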We plan to use the accuracy information from this trial to support a larger multi-institutional or randomized study of the use of the Breast Cancer Locator in patients with non-palpable breast cancer. We anticipate that the main outcome measure of the next, larger trial, like our current trial of the supine imaging/optical scan and intra-operative tracker system (D0928, phase II), will be the positive margin rate.

Secondary endpoints will be analyzed as follows. One secondary outcome measure will be the positive margin rate as defined by standard pathologic evaluation of the entire specimen. Our senior breast Pathologist, [name], has performed a detailed analysis of the surgical margins for patients who had a core biopsy which was positive for cancer or DCIS and then underwent partial mastectomy at Dartmouth in the year 2005. A total of 125 patients with invasive ductal carcinoma were identified: 31 (25%) had positive margins. Twenty six of 53 patients undergoing partial mastectomy for DCIS had positive margins (45%). Overall, 57/178 patients (32%) had positive margins. A two-thirds decrease in the positive margin rate (i.e., from 32% to 11% or less) would be clinically meaningful.

Another secondary outcome measure, the distances between the specimen edges as determined by the Breast Cancer Locator and by the supine MRI/optical scan/ tracker system, will be measured and descriptive statistics will be employed. We will conclude that the two methods of depicting the tumor edges on the breast skin surface are equivalent if the mean distances between the edges are < 5 mm.

We also wish to minimize the excision of normal breast tissue around the cancer. Lumpectomy specimen volumes will be measured and descriptive statistics employed. Measured specimen volumes will be compared to theoretical ideal specimen volumes generated by calculating the volume of the tumor specimen with 1 cm added to all of its surfaces based on the supine MRI.

Relevant data will be saved in Velos electronic case report forms.

Section 9. SAFETY AND DATA MONITORING

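### Meeting the 80%-in-20-patients stopping rule does not establish accuracy of at least 80%, and the plan attaches no interval to that proportion

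*Combined protocol and SAP*

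**What the plan says.** All of this is in Sections 7 and 8 of the combined protocol and SAP.

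- A patient counts as a success or a failure: "The BCL will be considered accurate if all 5 measurements are > 0 cm from the tumor edge".
- Accuracy is reviewed after 10 patients. Below 80%, the locator is modified and 10 more are tested. If that also falls short, "additional modifications may be made and additional patients may be accrued to this study up to a maximum of 50 patients".
- If a cohort of ten reaches 80% or more, "we will accrue an additional 10 patients to confirm the finding".
- Once accuracy is judged to be at least 80%, "in 20 patients we will terminate accrual".
- On limits to achievable accuracy, the plan says that, because MRI can under-size the tumor, "a positive margin (a distance of zero or less) would be expected in 5% of patients".
- It also allows that the device may have faults: "We may discover an unforeseen design flaw in the methodology or product manufacture".
- On use of the result: "We plan to use the accuracy information from this trial to support a larger multi-institutional or randomized study", in patients with non-palpable cancer.

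Descriptive statistics are named for secondary outcomes, for example "Lumpectomy specimen volumes will be measured and descriptive statistics employed". For the accuracy proportion that stops the study, the plan gives no interval, null rate, error rate or power, and no reporting by cohort or device version. It does not say whether confirmation means 8/10 in the second ten or 16/20 overall, or what follows a failed confirmation.

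**The concern.** The plan's wording treats an observed proportion of at least 80% in 20 patients as having settled that accuracy is at that level. Twenty patients cannot do that unless the result is perfect. A threshold rule also means that the passing figure tends to overstate the truth when true accuracy is near or below 80%, and each permitted restart gives a mediocre device another chance to pass.

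What is at stake is the claim carried forward. Section 5 explains that patients here are protected because resection is guided by palpation. The next study is in non-palpable cancer, where that protection is absent. A bare statement of at least 80% in 20 patients would pass on neither the imprecision nor the history of any failed cohorts.

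**Working it through.** **The plan's own figures.** The 80%, the 20 and the 50 are given without a derivation, so there is no power or error rate to reproduce. The one checkable figure is accrual time: 20/33 × 12 = 7.3 months, against the stated 8.

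**Inputs from Sections 7 and 8.** Cohorts of 10; a cohort qualifies at 8/10 or more; a pass is at least 80% in 20, that is 16/20; maximum 50 patients. A pass uses two tens, so (50 − 20)/10 = 3 failed tens can come before it. True accuracy p is assumed, because the documents give none beyond the expected 5% failure rate (p about 95%).

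**1. What a passing result supports.** Exact (Clopper-Pearson) 95% intervals, using beta quantiles B(0.025; x, n−x+1) and B(0.975; x+1, n−x):

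| Result | 95% interval |
|---|---|
| 16/20 | 56.3% to 94.3% |
| 17/20 | 62.1% to 96.8% |
| 18/20 | 68.3% to 98.8% |
| 19/20 | 75.1% to 99.9% |
| 20/20 | 83.2% to 100% |

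Only 20/20 has a lower limit above 80%.

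**2. How often the rule is met.** Let X and Y be independent Binomial(10, p) counts for the qualifying and confirming tens. Define a = P(X ≥ 8 and X+Y ≥ 16), the chance of passing in one attempt on the pooled reading; b = P(X < 8); and c = P(X ≥ 8) − a, the chance of qualifying and then failing confirmation. With k cohorts available and every restart used,

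S(k) = a + b·S(k−1) + c·S(k−2), with S(0) = S(1) = 0.

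At p = 70%, with modifications having no effect: a = 0.1920, b = 0.6172, c = 0.1908.

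- 20 patients: S(2) = 0.192
- 30 patients: S(3) = 0.1920 + 0.6172 × 0.1920 = 0.31
- 40 patients: S(4) = 0.1920 + 0.6172 × 0.3105 + 0.1908 × 0.1920 = 0.42
- 50 patients: S(5) = 0.1920 + 0.6172 × 0.4203 + 0.1908 × 0.3105 = 0.51

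If the second ten must itself reach 8/10, the figure by 50 patients is 0.40.

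**3. What is reported after a pass.** At p = 70%, passing totals of 16, 17, 18, 19 and 20 have probabilities 0.482, 0.334, 0.145, 0.036 and 0.004. Their mean is 16.75/20 = 83.7%. The value is the same for a single attempt, so the pass threshold creates the upward bias; restarts only raise how often a pass occurs. Of passes by 50 patients, 1 − 0.192/0.511 = 62% follow at least one failed cohort.

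**4. If the device is as good as hoped.** At p = 95%, a = 0.987 and the mean reported accuracy is 95.2%.

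**5. The confirmation wording.** On the pooled reading, 10/10 followed by 6/10 gives 16/20 and stops accrual. If the second ten must reach 8/10, it does not.

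**The case against.** The strongest reply is that this is an early device study with an accrual rule and no hypothesis test, so it makes no formal claim to defend. That is fair, and the 16/20 trigger can stay. But the text describes accuracy as having been determined at that level, and the plan carries the accuracy information into the next study, so the precision of the figure matters.

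A reader might infer several stronger criticisms that the documents do not support:

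- *That only a pass can end the study.* Accrual also ends at 50 patients. In the worst case above, 49% of trials at a true 70% would end there without a pass.
- *That 51% is the expected false-pass rate.* After a second failure the plan says further modification and accrual may happen, not that they will. The 51% assumes every restart is used, including after a failed confirmation, and that modifications do nothing. The plan bases modifications on review of each inaccurate case. If successive versions were 70%, 80%, 90% and 95% accurate, a version below 80% would pass 19% of the time, no more than in one attempt. With a slower 70%, 75%, 80%, 85%, the figure is 0.192 + (0.617 + 0.191) × 0.3455 = 47%.
- *That failed cohorts bias the estimate.* The threshold does that.
- *That device versions will be mixed in the final 20.* Modification is described only after inaccurate results, so a single version is implied. It is just not written as a requirement.
- *That failed cohorts will be left out of the report.* The plan is silent on this; it does not say so.

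Two further points stand. The measured distances are also accuracy information, although they do not supply the missing interval for the proportion. The next trial is expected to have its own main endpoint, the positive margin rate, which limits the damage from an optimistic figure here.

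**Conclusion.** The concern holds in a limited form. The rule is acceptable for deciding when to stop accrual, but meeting it does not show that accuracy is at least 80%. That conclusion rests on the exact intervals and needs no assumption about true accuracy. The pass rates do need one: they take p as constant, patients as independent and modifications as ineffective, and at p = 70% they run from 19% to 51% depending on how many restarts are used. At the hoped-for 95% the problem is negligible. The plan itself foresees possible design flaws and budgets up to 50 patients, so lower accuracy is a case worth planning for. This should be fixed, but it is no reason to hold up the trial, and it does not bear on the care of these participants.

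**What to change.** 1. Keep 16/20 or more as an accrual-stopping trigger only, and remove the statement that it determines accuracy to be at least 80%.
2. Report accuracy with exact 95% intervals for the final 20 and for every cohort and BCL version, passing or failing. An interval on the final 20 alone is not enough: in the 70% worst case, accuracy over all patients in passing trials would average 78%, against 84% in the final 20.
3. State that the 20 patients behind the accuracy figure must share one unmodified BCL version.
4. State whether confirmation means 8/10 in the second ten or 16/20 overall, and that a failed confirmation counts as a failed cohort.

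**Cost.** On the pooled reading, expected accrual does not change (20.1 patients at a true 95%, 28.9 at 80%). The intervals will be wide (8/10 gives 44% to 97%) and the headline less favourable. If the BCL were changed between the two tens, the count would restart, adding at least 10 patients, or 10/33 × 12 = 3.6 months at the plan's rate. Requiring 8/10 in the second ten is an option rather than a correction. At a true 80% it would lower the pass rate by 50 patients from 91% to 84% and raise expected accrual from 28.9 to 31.8.
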